6. STUDY PROCEDURE AND ASSESSMENTS

The first patient first visit (FPFV) is defined as the 1st visit performed at one of the clinical centers by the 1st screened patient. The last patient, last visit (LPLV) is defined as the last visit performed at one of the clinical centers by the last patient (i.e., the last visit foreseen by the study protocol), independently of whether the patient completed or withdrew from the study. The First Patient In (FPI) is defined as the first randomized patient at one of the clinical centers.

Patients will be evaluated according to the following scheme:

Interventional phase

- Screening visit (day -8),
- Baseline (day 1+2),
- Week 2 (day 14±2),
- Week 4 (day 28±2) or early exit

Follow up visits

- Week 8 (day 56±2)
- Week 12 (day 84±4)
- Week 16 (day 112±7)
- Week 24 (day 168±7)

The schedule of study procedures and assessments is tabulated by visit in the Schedule of Evaluations in § 2.0.

The descriptions of the procedures to be performed at each visit are provided below.

6.1. SCREENING AND RANDOMIZATION VISITS

During the screening visit (day -8) all procedures for will be performed. From the day of screening the patients will stop any kind of further ophthalmic treatment, until all of the final study evaluations have been completed, except preservative free artificial tears (wash out period from day -8 to baseline, Day 1 +2). The wash out period should not be less than 8 days and more than 10 days.

At the end of the screening period, patients meeting the entry criteria for this study will be randomized 1:1 and treated for 4 weeks with either cenegeamin ophthalmic solution 20 mcg/mL TID or vehicle TID.

Slit lamp examination and the fluorescein staining (Corneal and/or Conjunctival staining with Fluorescein) will be performed at different time-points, as specified in the section 2 of “SCHEDULE OF EVALUATIONS” and procedure will be detailed on the informed consent form.

An independent Blinded Reading Center (RC) will also be used to assess the images collected at protocol-specified time points and sent to the RC as specified in the RC procedure manual.

The RC will provide instructions for the slit lamp photography and the fluorescein staining procedures.

	Day	Procedures/Assessments
Screening visit	Day -8	
The following procedures will be performed (order below is mandatory):
 
 ➤ Explanation to the patient of study aims, procedures and possible risks ➤ Informed consent signature ➤ Screening number allocation ➤ Patient eligibility: Inclusion/exclusion criteria evaluation ➤ Pregnancy test for female patients of childbirth potential ➤ Demographic data ➤ Ocular and systemic medical history ➤ Previous ocular and systemic medications (prior to start the study) ➤ Ocular examination of both eyes, to be performed by the physician investigator: 
 • Assessment by SANDE questionnaire • Assessment by IDEEL questionnaire • Assessment of best corrected distance visual acuity (BCDVA) • External Ocular Examination • Schirmer test I (without anesthesia) • Slit-lamp examination (SLE) to assess the eyelid (Meibomian glands), eyelid (erythema), eyelid (edema), lashes, conjunctiva erythema, lens, iris, anterior chamber, corneal horizontal diameter • TFBUT • Ocular surface staining (NEI score - corneal and conjunctival fluorescein staining) • ➤ AE collection ➤ Preservative free artificial tears dispensation 
The Investigator will dispense to the patients the preservative free artificial tears (Blink® Tears or equivalent), provided by Sponsor, to be used only if strictly needed by the patient (the patient must follow the instruction in the product leaflet). The patients will be instructed to enter information of self-administration of Blink® Tears or equivalent (if the administration has been occur per eye) and AE occurrence into the diary.
 
The diary will be given from the PI or delegate during this visit.

At home	Day -8 – Day 1+2 (baseline)	
 ➤ Recording any unusual medical conditions - AE monitoring (diary) ➤ Artificial tears use during the wash-out period (diary) 
Data will be recorded by the patient on the patient's diary.

	Day	Procedures/Assessments

Visit 1 Baseline	Day 1 +2	
The following procedures will be performed (order below is mandatory):
 
 ➤ Pregnancy test for female patients of childbirth potential ➤ Previous ocular and systemic medications (prior to start the treatment) ➤ Ocular examination of both eyes to be performed by the physician investigator: 
 • Assessment by SANDE questionnaire • Assessment by IDEEL questionnaire • Assessment of best corrected distance visual acuity (BCDVA) • External Ocular Examination • Schirmer test I (without anesthesia) • Slit-lamp examination (SLE) to assess the eyelid (Meibomian glands), eyelid (erythema), eyelid (edema), lashes, conjunctiva erythema, lens, iris, anterior chamber, corneal horizontal diameter • TFBUT • Ocular surface staining (NEI score – corneal and conjunctival fluorescein staining) • Schirmer test II (with Anesthesia) 
 ➤ Patient eligibility: Inclusion/exclusion criteria evaluation ➤ Randomization ➤ Study drug dispensation ➤ Preservative free artificial tears dispensation ➤ AE collection 
During visit 1, Day 1+2 or baseline, PI or delegate must check and collect the patient's diary concerning the screening period and provide a new diary for the treatment period. The PI or a delegate must check if patient has correctly completed the diary. If not, the site staff must retrain the patient.
 
The Investigator will dispense to the patients their monthly box containing the study drug for the following 4 weeks together with an adequate number of adapters and pipettes.
 
The Investigator will dispense to the patients the preservative free artificial tears (Blink® Tears or equivalent), provided by Sponsor, to be used only if strictly needed by the patient (the patient must follow the instruction in the product leaflet).
 
After completing baseline evaluation patients will be administered, by PI, with the study treatment as per instructions, and will self-administer at home the subsequent doses. Patients will return to the clinical site on Day 14 (±2) (Week 2, visit 2).

6.2. STUDY VISITS AND FOLLOW-UP ASSESSMENTS

After the first two weeks of treatment the patient will undergo a medical assessment during the visit 2 (week 2). Following the completion of the double-blind treatment (visit 3, week 4), patients will be followed up for efficacy until visit 6 (week 16) and safety assessments until visit 7 (week 24). During the follow-up period until

week 12 patients will not use further ophthalmic treatment except preservative free artificial tears, provided by Sponsor, one drop instilled in both eyes three times daily (morning, afternoon and evening). The patient, only if strictly needed, can administer additional drops and must document in the patient's diary the n° of additional drops administered for each eye. After week 12 (visit 5), patients will be followed-up for additional 12 weeks until the end of the study (visit 7, week 24) during which patients can use others artificial tears different from the artificial tears provided by the Sponsor.

Slit lamp examination and the fluorescein staining (Corneal and/or Conjunctival staining with Fluorescein) will be performed at different time-points, as specified in the section 2 of "SCHEDULE OF EVALUATIONS" and procedure will be detailed on the informed consent form.

An independent Blinded Reading Center will also be used to assess the images collected, as described in the previous paragraph.

	Day	Procedures/Assessments
At home	Days 1-14 ±2	
 ➤ Self-administration at home of the IMP, three times daily every 6 h for both eyes (diary) ➤ Recording any new or changes in concomitant medications (diary) ➤ Recording any unusual medical conditions - AE monitoring (diary) ➤ Recording possible use of preservative free artificial tears (diary). 
Data will be recorded by the patient in the patient's diary.

	Day	Procedures/Assessments
Visit 2 Week 2	Day 14±2	
The following procedures will be performed (order below is mandatory):
 
 ➤ Ocular examination of both eyes to be performed by the physician investigator: 
 • Assessment by SANDE questionnaire • Assessment by IDEEL questionnaire • Assessment of best corrected distance visual acuity (BCDVA) • External Ocular Examination • Schirmer test I (without anesthesia) • Slit-lamp examination (SLE) to assess the Eyelid - Meibomian glands, Eyelid – Erythema, Eyelid - Edema Lashes, Conjunctiva Erythema, Lens, Iris, Anterior Chamber, Corneal Horizontal Diameter • TFBUT • Ocular surface staining (NEI score - corneal and conjunctival fluorescein staining) • ➤ Concomitant ocular and systemic medications ➤ Frequency of patient's artificial tear use during first 2 weeks of treatment (to be reported in eCRF) ➤ AE monitoring 
During the visit 2, week 2, the patient must bring the diary assigned during the previous visit. The PI or a delegate must check if patient has correctly completed the diary. If not, the site staff must retrain the patient.
 
At completion of the assessment the patient will be discharged and will be asked to return for the end of treatment visit on day 28±2 (Visit 3 week 4).
 
The Investigator will dispense to the patients the preservative free artificial tears (Blink® Tears or equivalent), provided by Sponsor, to be used only if strictly needed by the patient (the patient must follow the instruction in the product leaflet).

At home	Days 14 ±2 – 28 ± 2	
 ➤ Self-administration at home of the IMP, three times daily every 6 h for both eyes (diary) ➤ Recording any new or changes in concomitant medications (diary) ➤ Recording any unusual medical conditions - AE monitoring (diary) ➤ Recording possible use of preservative free artificial tears (diary). 
Data will be recorded by the patient on the patient's diary.

	Day	Procedures/Assessments
Visit 3 week 4	Day 28±2	
The following procedures will be performed (the below order is mandatory):
 
 ➤ Pregnancy test for female patients of childbirth potential ➤ Ocular examination of both eyes to be performed by the physician investigator: 
 • Assessment by SANDE questionnaire • Assessment by IDEEL questionnaire • Assessment of best corrected distance visual acuity (BCDVA) • External Ocular Examination • Schirmer test I (without anesthesia) • Slit-lamp examination (SLE) to assess the Eyelid - Meibomian glands, Eyelid – Erythema, Eyelid - Edema Lashes, Conjunctiva Erythema, Lens, Iris, Anterior Chamber, Corneal Horizontal Diameter • TFBUT • Ocular surface staining (NEI score - corneal and conjunctival fluorescein staining) • Schirmer Test II (with Anesthesia) ➤ Assessment of compliance to treatment (from patient diary and IMP reconciliation from returned weekly boxes) ➤ Concomitant ocular and systemic medications ➤ Frequency of patient's artificial tear use during the last 2 weeks of treatment (to be reported in eCRF). ➤ AE monitoring ➤ Verify patient study medication dosing compliance 
During visit 3, week 4, PI or delegate must check and collect the patient's diary concerning the treatment period and provide a new diary for the follow up period. At completion of the assessment the patient will be discharged and will be asked to return for the follow up visit on day 56±2 (Visit 4 week 8). The Investigator will dispense to the patients the preservative free artificial tears (Blink® Tears or equivalent), provided by Sponsor, to be self-administered three times daily, one drop in both eyes during the first 4 weeks of Follow up. The PI or delegate has to explain to the patients that, only if strictly needed, they can administer an additional numbers of drops of Blink® Tears or equivalent, by documenting all information in the patient's diary.

At home	Days 28 ±2 – 56 ± 2	
 ➤ Recording any new or changes in concomitant medications (diary) ➤ Recording any unusual medical conditions - AE monitoring (diary) ➤ Artificial tears use during 4 weeks of FU (diary) 
Data will be recorded by the patient on the patient's diary.

	Day	Procedures/Assessments
Visit 4 Follow up week 8	Day 56± 2	
The following procedures will be performed (the below order is mandatory):
 
 ➤ Ocular examination of both eyes to be performed by the physician investigator: 
 • Assessment by SANDE questionnaire • Assessment by IDEEL questionnaire • Assessment of best corrected distance visual acuity (BCDVA) • External Ocular Examination • Schirmer test I (without anesthesia) • Slit-lamp examination (SLE) to assess the Eyelid - Meibomian glands, Eyelid – Erythema, Eyelid - Edema Lashes, Conjunctiva Erythema, Lens, Iris, Anterior Chamber, Corneal Horizontal Diameter • TFBUT • Ocular surface staining (NEI score - corneal and conjunctival fluorescein staining) ➤ Concomitant ocular and systemic medications ➤ Frequency of patient's artificial tear use during 4 weeks of FU (to be reported in eCRF). ➤ AE monitoring 
During visit 4, week 8, PI or delegate must check the patient's diary concerning the follow up period.
 
The Investigator will dispense to the patient the preservative free artificial tears (Blink® Tears or equivalent), provided by Sponsor, to be self-administered three times daily, one drop in both eyes during the second 4 weeks of Follow up. The PI or delegate has to explain to the patients that, only if strictly needed, they can administer an additional numbers of drops of Blink® Tears or equivalent, by documenting all information in the patient's diary.

At home	Days 56 ±2 – 84 ± 4	
 ➤ Recording any new or changes in concomitant medications (diary) ➤ Recording any unusual medical conditions - AE monitoring (diary) ➤ Artificial tears use during 4 weeks of FU (diary) 
Data will be recorded by the patient on the patient's diary.

	Day	Procedures/Assessments
Visit 5 Follow up week 12	Day 84 ± 4	
The following procedures will be performed (the below order is mandatory):
 
 ➤ Ocular examination of both eyes to be performed by the physician investigator: 
 • Assessment by SANDE questionnaire • Assessment by IDEEL questionnaire • Assessment of best corrected distance visual acuity (BCDVA) • External Ocular Examination • Schirmer test I (without anesthesia) • Slit-lamp examination (SLE) to assess the Eyelid - Meibomian glands, Eyelid – Erythema, Eyelid - Edema Lashes, Conjunctiva Erythema, Lens, Iris, Anterior Chamber, Corneal Horizontal Diameter • TFBUT • Ocular surface staining (NEI score - corneal and conjunctival fluoresce instaining) ➤ Concomitant ocular and systemic medications ➤ Frequency of patient's artificial tear use during 4 weeks of FU (to be reported in eCRF). ➤ AE monitoring 
During visit 5, week 12, PI or delegate must check and collect the patient's diary concerning the follow up period and provide a new diary for the second follow up period.
 
The Investigator will instruct the patient that during the follow up period (from week 13 to week 24) other topical treatments will be allowed at discretion of the treating physician. Such treatments will be recorded by the investigators.
 
The patient has to register the use other preservative free artificial tears in the patient's diary.

At home	Days 84 ± 4 – 168 ± 7	
 ➤ Recording any new or changes in concomitant medications (diary) ➤ Recording any unusual medical conditions - AE monitoring (diary) ➤ Artificial tears use during 4 weeks of FU (diary) 
Data will be recorded by the patient on the patient's diary.

	Day	Procedures/Assessments
Visit 6 Follow up week 16	Days 112 ± 7	
The following procedures will be performed (the below order is mandatory):
 
 ➤ Pregnancy test for female patients of childbirth potential ➤ Ocular examination of both eyes to be performed by the physician investigator: 
 • Assessment by SANDE questionnaire • Assessment by IDEEL questionnaire • Assessment of best corrected distance visual acuity (BCDVA) • External Ocular Examination • Schirmer test I (without anesthesia) • Slit-lamp examination (SLE) to assess the Eyelid - Meibomian glands, Eyelid – Erythema, Eyelid - Edema Lashes, Conjunctiva Erythema, Lens, Iris, Anterior Chamber, Corneal Horizontal Diameter • TFBUT • Ocular surface staining (NEI score - corneal and conjunctival fluorescein staining) • ➤ Concomitant ocular and systemic medication ➤ Frequency of patient's artificial tear use during 4 weeks of FU (to be reported in eCRF) ➤ AE monitoring 
PI or delegate must check the patient's diary concerning the previous follow up period.

Visit 7 Follow up week 24 Final visit or early termination visit (ETV)	
Days 168 ± 7
 
The End of Study (EoS) visit is defined as the last follow-up at week 24. In case of premature study discontinuation, patients will undergo an Early Termination Visit (ETV).
 
 ➤ Concomitant ocular and systemic medication ➤ Frequency of patient's artificial tear use during 8 weeks of FU (to be reported in eCRF) ➤ AE monitoring 
PI or delegate must check and collect the patient's diary concerning the last follow up period.

---	--

6.3. EARLY WITHDRAWAL FROM THERAPY OR ASSESSMENT

6.3.1. Primary Reason For Discontinuation From The Study

A premature discontinuation will occur when a patient who signed the ICF ceases participation in the study, regardless of circumstances, before the completion of the study protocol procedures. Patients can be prematurely discontinued from the study for one of the following reasons:

- **Adverse event (AE):** Any significant AE that, in the opinion of the Investigator or concerned patient, is not compatible with study continuation.
- **Disease progression or worsening,** that according to the opinion of the Investigator is not compatible with study continuation..
- **Death.**
- **Lost to follow-up** (Every effort must be made to contact the patient; a registered letter must be sent).
- **Non-compliance with study drug:** an indication that a patient has not agreed with or followed the instructions related to the study medication.
- **Severe Protocol violation:** an event or decision that stands in contrast to the guidelines set out by the protocol.

- **Study terminated by the Sponsor:** an indication that a clinical study was stopped by Sponsor.
- **Withdrawal of consent:** study discontinuation requested by a patient for whatever reason.
- **Other reasons,** such as administrative reasons or pregnancy.

Before removal, each case should first be discussed with Dompé farmaceutici S.p.A.

The reasons for premature discontinuation from the study will be reflected on the Study Termination Record of the eCRF. Unless the patient has withdrawn consent, the follow up visit assessments should be performed as detailed in § 6.

The investigator should advise patients that prematurely discontinue on any therapies or treatments for their condition and refer them for further treatment as appropriate

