6.3.2. Discontinuation procedures

Treatment discontinuation

Patients who discontinue the treatment will not be withdrawn from the study by default, but will be asked to complete safety and efficacy observations as per the protocol, unless otherwise they withdraw their consent.

Study discontinuation

For any patient discontinuing the study following randomization, the Investigator will:

- ask the patient to undergo, as far as possible, a final medical visit (Early Termination Visit - ETV) to examine the patient's health conditions. This examination will verify that all values tested at screening have remained within a clinically acceptable range (i.e., not clinically significant changes compared to screening).
- arrange for alternative medical care of the withdrawn patient, if necessary.
- report in the eCRF date and time of the last dose administration, and date and primary reason of study discontinuation.
- record in the eCRF any follow-up if the patient is withdrawn for an AE. AE's should be followed until resolution.

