8.7. PREGNANCY IN THE CLINICAL TRIAL

Women of childbearing potential are not excluded from the study as long as adequate birth control methods are being utilized. Women of childbearing potential are defined as all women physiologically capable of becoming pregnant. Adequate birth control methods are summarized in the protocol's exclusion criteria.

Prior to enrollment in the clinical trial, female patients of childbearing potential and their partners must be advised of the importance of avoiding pregnancy during the entire course of the study treatment and for the 30 days after the study treatment period ends and of the potential risks associated with an unintentional pregnancy. During the trial (during the study treatment period and during the follow up), female patients are to be instructed to contact the Investigator immediately if they suspect they might be pregnant; in the same way, male patients who become aware that the partner might be pregnant, are to be instructed to contact the Investigator immediately.

The Investigator must report every pregnancy on a pregnancy report form as soon as possible (within 24 hours of learning of the pregnancy) to **PPD**/Dompé Drug Safety contacts reported at Paragraph 8.4.1, even if no AE has occurred, and follow it to term.

The pregnancy form will be utilized to capture all pregnancy-related information until the birth of the child for both the patient and the partner.

If the pregnancy is associated with a SAE (e.g. if the mother is hospitalized for dehydration), in addition to the pregnancy report form, a separate SAE report form must be filed as described in § 8.4 with the appropriate serious criterion (e.g. hospitalization) indicated on the SAE report form. Miscarriage, stillbirth and any malformation/disease must be reported as a SAE. Any pregnancy leads to the immediate cessation of the study treatment.

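### Protocol 6.2, 6.3.1 and 6.3.2 conflict on what is collected after a patient leaves the study, and one reading loses co-primary values for outcome-related reasons

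*Protocol*

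**What the plan says.** Protocol 6.3.1 defines premature discontinuation as ceasing to take part in the study, then states: "Patients can be prematurely discontinued from the study for one of the following reasons". The reasons include an AE or worsening that the investigator thinks incompatible with continuing, severe protocol violation, and non-compliance with study drug, described as "an indication that a patient has not agreed with or followed the instructions related to the study medication". The sponsor is consulted on each case ("Before removal, each case should first be discussed with" the sponsor). Near the end the section adds: "Unless the patient has withdrawn consent, the follow up visit assessments should be performed as detailed in § 6".

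Protocol 6.3.2 treats two situations separately.

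- **Stopping treatment:** "Patients who discontinue the treatment will not be withdrawn from the study by default". These patients are asked to complete the safety and efficacy observations.
- **Leaving the study:** the investigator is to "ask the patient to undergo, as far as possible, a final medical visit (Early Termination Visit - ETV". That visit is to check every value tested at screening, and the screening list in 6.1 includes both Schirmer I and SANDE.

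Protocol 6.2 puts the ETV in the same row as Visit 7 (Week 24). That row lists concomitant medication, artificial-tear use, AEs and the diary, but neither Schirmer I nor SANDE. The section 2 schedule has no ETV column and marks neither measure at Visit 7. The synopsis and section 6 attach early exit to the Week 4 visit, which does include both measures. Section 3.3.1 also allows discontinuation for insufficient response or worsening, without saying whether from drug or from study.

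The primary estimand (Protocol 9.4.2, SAP 7.3) is treatment policy: observed values count whatever intercurrent events occur.

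**The concern.** A treatment-policy estimand depends on measuring patients after they stop drug, respond poorly or have an AE. Section 6.3.1 lists just these events as reasons to leave the study, and the three sections then tell sites different things about what to measure afterwards. Nothing says which section governs.

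If a site takes the ETV as the last contact, a patient who leaves because of worsening, an AE or non-compliance has no later scheduled Schirmer I or SANDE. The resulting gaps would be related to outcome. The imputation step would suffer as well. MI-RD learns only from retrieved drop-outs, defined in Protocol 9.4.3.1 and SAP 10.1.2 as patients who stop treatment but remain in the study. A patient who stops drug and is also taken out of the study cannot be one, so the same reading creates missing values and removes the data meant to impute them.

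**Working it through.** **1. The plan's own figures.** These come from SAP section 5: 45 evaluable patients per arm, one-sided alpha 0.025, responder rates 35% and 5%, SANDE difference 15 with SD 20.

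- Schirmer I, pooled test with mean rate 0.20. Null SE = sqrt(2 × 0.20 × 0.80 / 45) = 0.0843. Alternative SE = sqrt((0.05 × 0.95 + 0.35 × 0.65) / 45) = 0.0782. z = (0.30 − 1.96 × 0.0843) / 0.0782 = 1.72, so power is 95.8%, as stated.
- SANDE, two-sample t-test. Noncentrality = 15 / (20 × sqrt(2/45)) = 3.56 on 88 df, so power is 94.0%, as stated.
- Overall: 0.958 × 0.940 = 0.9005, the stated 90%. Enrolment: 90 / 0.90 = 100.

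All reproduce, and the wording conflict changes none of them.

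**2. The instructions side by side,** for a patient removed for worsening before the Week 4 visit:

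| Source | What is asked | Schirmer I at Week 4 | SANDE at Week 12 |
|---|---|---|---|
| 6.3.1, close | Section 6 follow-up unless consent is withdrawn | Collected | Collected |
| 6.3.2, study exit | One final visit covering the screening values | Once, at exit | Once, at exit |
| 6.2, Visit 7/ETV row | Medication, tear use, AEs, diary | Not listed | Not listed |
| Synopsis and section 6 | Early exit paired with Week 4 | Once, at exit | Once, at exit |

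Only the first row delivers both co-primary values on schedule. For a patient who leaves after the Week 4 visit, Schirmer I is already in hand and only SANDE is at stake.

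**3. Effect on MI-RD.** This applies to patients who leave during the four treatment weeks. Someone who completes treatment and leaves between Weeks 4 and 12 loses the SANDE value but would not have been a retrieved drop-out in any case. If too few retrieved drop-outs remain for the model to converge, SAP 10.1.2 switches to Copy Reference.

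**4. Size.** The documents give neither a removal rate nor a split by reason. Purely as an illustration, assume that a share m of the cenegermin arm lacks each co-primary value and is imputed at vehicle level, as under Copy Reference. With 50 per arm, the expected cenegermin responder rate is 0.05 + 0.30(1 − m) and the SANDE difference is 15(1 − m).

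| m (assumed) | Responder rate | SANDE difference | Joint power |
|---|---|---|---|
| 0% | 35% | 15 | 93.8% |
| 5% | 33.5% | 14.25 | 91.0% |
| 10% | 32% | 13.5 | 87.3% |
| 20% | 29% | 12 | 76.9% |
| 30% | 26% | 10.5 | 62.6% |

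These are products of two normal-approximation powers, ignoring imputation variance. Here m is missingness from all causes. How much of it the wording would cause is unknown, so the table shows sensitivity to missing data and not the effect of this conflict.

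**The case against.** The strongest reply is that the protective sentence is already there. It stands in 6.3.1 directly after the instruction to record the reason for leaving, and its only exception is withdrawal of consent. Section 6.3.2 never says that the ETV replaces scheduled visits, so it can be read as an addition. The phrase about not being withdrawn by default is itself protective: stopping drug does not trigger exit. Sponsor consultation before removal, and the retention measures in Protocol 9.4.7 and SAP 7.8, point the same way. All of this stands, and it makes the loss a risk rather than a consequence.

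It does not remove the conflict. A visit described as final sits uneasily with continued follow-up, and the two accounts of ETV content cannot both be right.

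A reader might infer three stronger things that the documents do not support.

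- **That the estimand is contradicted.** It is not. It uses what is observed, and uncollected values go to MI-RD or Copy Reference, with MAR and tipping-point analyses behind them. Those analyses test assumptions about missing values; they do not recover them.
- **That an ETV outside the Week 4 or Week 12 window can never supply a co-primary value.** SAP 4.4 assigns data by the visit at which they were collected and has no window exclusion. An early exit recorded at the Week 4 visit might therefore be analysed as Week 4.
- **That patients who merely stop drug are lost.** Section 6.3.2 keeps them in efficacy follow-up.

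**Conclusion.** The conflict is in the current text and affects both co-primary endpoints. Under the close of 6.3.1 nothing is lost. Under 6.2, or under 6.3.2 read as a single last visit, values go missing for reasons tied to outcome, and the retrieved drop-out pool shrinks by those who leave during treatment. Which reading sites would follow is not known.

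The size cannot be estimated from the documents. The stated power and the enrolment of 100 stand, and the plan already allows for 10% not evaluable. This is a cheap improvement that removes an avoidable source of bias; it is not a flaw that invalidates the primary analysis.

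**What to change.** 1. In 6.3.1, with a cross-reference in 3.3.1, state that AE, worsening, insufficient response, non-compliance and protocol violation are reasons to stop study drug. Scheduled visits through Weeks 4, 12 and 16 continue unless the patient withdraws consent, dies or is lost to follow-up, the sponsor ends the study, or the investigator judges further assessments unsafe. After Week 4 there is no drug left to stop, so these events alone should not end the visits.
2. In 6.3.2, state that the ETV does not replace the visits required by the close of 6.3.1, and is the last visit only for patients who will not or cannot continue.
3. In 6.2, separate the ETV from the Visit 7 row and list Schirmer I and SANDE for the ETV only, so that Week 24 completers have no added tests.

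The cost is wording in four protocol sections, no new scheduled visits, and two quick assessments at the ETV. Some non-adherent patients are followed longer, which the close of 6.3.1 already asks. Investigators keep full freedom to stop drug and keep a safety exit from assessments.
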